### **Other efficacy variables**

Other efficacy variables will comprise:

1. Time to moderate or marked improvements in dyspnea by Likert scale through Day 5
2. Dyspnea by VAS-AUC changes through Day 5
3. Length of stay in index ICU/CCU
4. Renal dysfunction & prevention of in-hospital worsening of renal function through Day 5
5. Time to re-hospitalization due to HF and renal failure through Day 180
6. Time to CV death or re-hospitalization due to HF/RF through Day 180
7. Time to in-hospital worsening heart failure through Day 5 where the in-hospital worsening heart failure is defined by symptoms only, signs only, and by both symptoms and signs
8. Use of loop diuretics and vasoactive agents through Day 5
9. Changes in cardio-renal biomarkers (Days 2 and 5)

Time to moderate or marked improvements in dyspnea by Likert scale through Day 5 (variable number 1) will be analyzed by Wilcoxon rank-sum test. Other time to event variables (5, 6 and 7) will be analyzed by presenting Kaplan-Meier estimates and testing with the log rank test. Change from baseline variables (2) will be analyzed using ANCOVA model with baseline VAS as a covariate. Variables representing the number of days or multi-categorical variables (3) will be analyzed using the Wilcoxon rank-sum test. The categorical variables (4 and 8) will be analyzed using chi-squared tests.

Detailed biomarker analyses (9) (changes in cardio-renal biomarkers at Days 2 and 5) will be included in the Statistical Analysis Plan.

### 9.5.2 Safety variables

The incidence of AEs recorded through Day 5 and the incidence of SAEs recorded through Day 14 will be presented for the Safety Set. Incident AEs will be considered those AEs with an onset date and time *after* the initiation of study drug. Adverse events with an onset between informed consent and study drug initiation will be listed separately. Adverse events will be coded using MedDRA. All reported AEs will be summarized by system organ class (SOC) and preferred term by treatment groups. Serious AEs (SAEs) will be summarized similarly.

In addition, AEs will be summarized by time period of onset: from study drug initiation up to and including Day 5, or from Day 6 up to and including Day 14. After Day 14 only suspected serious adverse events will be collected and reported to Novartis. Additionally, a summary of AEs by preferred term and severity, using the worst reported severity grade for each event for the subject, will be provided. For analysis purposes, all AEs defined as “definite”, “probable” or “possible” will be considered as related. If the relationship to study drug is unknown or missing, the AE will be considered to be drug-related. All study-drug-related AEs, AEs with an outcome of death, AEs leading to discontinuation of treatment, and study-drug-related SAEs, SAEs with an outcome of death, and SAEs leading to study drug discontinuation will be summarized by percentages and frequencies. Percentages will be based on the number of patients in the Safety Set. For the analysis by time period of onset, the percentages will be based on the number of patients in the Safety Set with the corresponding AE form completed.

Laboratory data will be summarized by presenting shift tables using extended normal ranges (baseline to most extreme post-baseline value), summary statistics of raw data and change from baseline (means, medians, standard deviations, 1st and 3rd quartiles, Q1 and Q3) and by flagging of notable values in data listings.

For vital signs, descriptive statistics will be provided for values and change from baseline at each assessment time point for pulse, respiratory rate, body temperature, and weight. Treatment groups will be compared for changes from baseline using t-tests.

The number and proportion of patients who experience a confirmed blood pressure decrease event during study drug administration will be provided. Among patients who experience a confirmed blood pressure decrease event, the events will be further characterized. Summaries will be provided separately for those confirmed events that resulted in study drug dose reduction, and those that resulted in study drug discontinuation. The possible interaction between the effect of serelaxin and the effect of IV nitrate administration within the first 48 hours will be examined.

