h A complete physical examination will be performed at screening; an abbreviated physical examination will be performed at all other specified time points. Refer to [Section 6.5.1](#)

i In addition to at screening and baseline, BP and HR (pulse) measurements are to be performed at 30 and 60 minutes and then every hour for the first 6 hours of study drug infusion, and then every 3 hours during study drug infusion, including night time hours. Post-infusion, BP and HR are to be measured every 3 hours until 12 hours following end of infusion, then every 6 hours for up to 48 hours and then every 24 hours until the earlier of Day 5 or Discharge. In addition BP and HR measurements will be taken at Day 60, and Day 180 as part of vital signs assessment. BP and HR are to be measured with the patient in the same position and with the same equipment using the same arm, throughout study drug infusion. These measurements may be made and recorded by trained healthcare personnel as part of their routine clinical duties, as well as study personnel. The assessments made as per the table above would be entered in the CRFs. Assessments at other time points will be part of source document. Refer to [Section 6.5.2](#)

j Blood will be locally collected at screening . Refer to [Section 6.5.3](#)

k Blood will be collected for measurement of biochemistry, hematology and samples shipped to the central laboratory for analysis. Refer to [Section 6.5.3](#).

m AEs will be collected from the signing of the ICF to and including Day 5. SAEs will be collected from the signing of the ICF to and including Day 14. After this period, only suspected SAEs will be collected.

lUrine dipstick will be measured locally at screening to rule out any conditions requiring further diagnostic evaluation or treatment. Refer to [Section 6.5.3.4.](#) .

n ECGs will be performed and interpreted locally at screening, at 48 hours, and at Day 5 or discharge, whichever occurs first. The ECG interpretation and person interpreting the ECG must be recorded in the source documents and in the eCRF Refer to [Section 6.5.4..](#)

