### **6.5.2 Vital signs**

Body temperature and respiration rate will be measured at Screening, Baseline, at 24 and 48 hours after start of study drug infusion and daily until Day 5 or discharge and on Days 60 and 180. Patients discharged prior to Day 5 will return to the hospital/clinic for Day 5 procedures.

BP and heart rate (pulse) measurements will be performed at Screening, throughout study drug infusion at 30 and 60 minutes, then every hour for the first 6 hours, and then every 3 hours, including night time hours. Post-infusion, BP and HR are to be measured every 3 hours until 12 hours following end of infusion, then every 6 hours for up to 48 hours and then every 24 hours until the earlier on Day 5 or discharge and at Days 60 and 180. BP and HR are preferred to be measured with the patient in the same position and with the same equipment using the same arm throughout study drug infusion. If different instruments are used, then calibration of these instruments is required and logs are documented by the site and verified by the monitor. These measurements may be made and recorded by trained healthcare personnel as part of their routine clinical duties, as well as study personnel. If at any time during dosing, the subject's systolic blood pressure is decreased by  $> 40$  mm Hg from baseline but is  $\geq 100$  mmHg in 2 consecutive measurements 15 min apart, serelaxin infusion rate will be decreased by 50% for the remainder of the 48 hour study drug administration. Serelaxin administration will be permanently discontinued at any time if in 2 consecutive measurements; 15 minutes apart, systolic blood pressure is reduced to  $< 100$  mmHg (also see details in [Section 5.5.5](#)).

Should the study drug dose be decreased or the study drug be discontinued prematurely due to blood pressure decrease, measurements should be taken every half hour through 2 hours following the blood pressure decrease event, and then hourly through 5 hours after event onset. Upon completion of the 5 hour post event onset time point, heart rate and blood pressure measurements should be resumed as outlined above.

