#### **9.5.8 Biomarkers**

Summary statistics for the baseline values, the post-baseline values, and the change from baseline will be provided by treatment group for the FAS and Safety Set.

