2.2 Efficacy evaluation

The Full Analysis Set (FAS) is the primary analysis population for efficacy analyses, following the intention-to-treat principle. Per-protocol (PPS) population will be used in the supportive analysis for primary and key secondary efficacy parameters (Table 2-5).

Table 2-5 List of efficacy endpoints and analyses

Endpoint	Analysis set	Analysis method
Primary efficacy endpoint ($\alpha=0.025$, 1-sided)		
1 Trichotomous composite (success, failure, no change)	FAS/PPS	Ordered logistic-regression (proportional odds) model that includes treatment and [REDACTED] as factors (primary analysis is on FAS)
	FAS	Ordered logistic-regression model including treatment only (sensitivity analysis 1)
	FAS	van Elteren extension of the Wilcoxon test stratified by [REDACTED] (sensitivity analysis 2)
Secondary efficacy endpoints (if primary endpoint is significant, then test in the order listed below at $\alpha=0.05$ each)		
1 Time (hours) to WHF through Day 5	FAS/PPS	Gehan's generalized Wilcoxon test
2 Time (days) to CV death through Day 180	FAS/PPS	Kaplan-Meier estimates and log-rank test
3 Time (days) to all-cause death through Day 180.	FAS	Kaplan-Meier estimates and log-rank test
Other efficacy endpoints (at $\alpha=0.05$, no multiplicity adjustment)		
1 Time (hours) to moderate or marked improvements in dyspnea by Likert scale through Day 5	FAS	Wilcoxon rank-sum test
2 Dyspnea by VAS-AUC changes (from baseline) through Day 5	FAS	ANCOVA
3 Length of stay (# of days) in index ICU/CCU	FAS	Wilcoxon rank-sum test
4 Renal dysfunction or worsening of renal function through Day 5	FAS	chi-squared test
5 Time (days) to re-hospitalization due to HF and renal failure through Day 180	FAS	Kaplan-Meier estimates and log rank test
6 Time (days) to CV death or re-hospitalization due to HF/RF through Day 180	FAS	Kaplan-Meier estimates and log rank test
7 Time to in-hospital worsening heart failure through Day 5 defined by symptoms and signs		Kaplan-Meier estimates and log rank test
8 Use of loop diuretics and vasoactive agents through Day 5	FAS	chi-squared test
9 Changes in cardio-renal biomarkers (Day 2 and Day 5)	FAS	Summary statistics, see Section 2.2.3

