2.4.3 Vital signs

For vital signs, descriptive statistics will be provided for values and change from baseline at each assessment time point for pulse, respiratory rate, body temperature, and weight. Treatment groups will be compared for changes from baseline using t-test.

Blood pressure and pulse during 48 hours drug infusion and 48 hours post infusion will also be listed.

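### Vital-sign changes are compared by t-test on the change score; ANCOVA with the recorded baseline as covariate would be at least as precise, at almost no cost (minor)

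*Protocol*

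**What the plan says.** Protocol section 9.5.2 gives the between-arm rule for vital signs: "Treatment groups will be compared for changes from baseline using t-tests". SAP section 2.4.3 has the same rule: "Treatment groups will be compared for changes from baseline using t-test". In both, the preceding sentence names the variables; in the SAP they are summarized "at each assessment time point for pulse, respiratory rate, body temperature, and weight". Blood pressure is not in that list.

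The baseline values exist. For temperature and respiration, protocol section 6.5.2 states: "Body temperature and respiration rate will be measured at Screening, Baseline, at 24 and 48 hours after start of study drug infusion". For pulse, a footnote to Table 6-1 states: "In addition to at screening and baseline, BP and HR (pulse) measurements are to be performed at 30 and 60 minutes". SAP section 2.1.3 substitutes the last screening value when a baseline value is missing.

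Elsewhere the plan does use baseline as a covariate. For the dyspnea VAS-AUC, protocol section 9.5.1 (other efficacy variables) says "Change from baseline variables (2) will be analyzed using ANCOVA model with baseline VAS as a covariate", and SAP section 2.2.3 agrees. Protocol section 9.2 and SAP section 2.1.6 also allow supplemental covariate-adjusted models, but only if an imbalance appears and only for efficacy. Neither document provides a baseline-adjusted model for vital signs.

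**The concern.** A change score assumes that each unit of baseline difference carries through in full to follow-up. Patients are randomized within 16 hours of presentation, while acutely unwell, and are then followed through recovery. For pulse and respiratory rate in particular, a slope of follow-up on baseline below 1 is plausible. Two things follow from a slope b below 1. The between-arm difference has more variance than the data require. And a chance baseline difference d between arms is over-corrected by (1 - b)d in the realized comparison, although this averages to zero over randomizations.

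These t-tests are the only planned between-arm tests of the four listed variables. In a safety comparison, lost precision makes a real difference easier to miss. At stake is the width of those intervals, and nothing in the confirmatory analysis.

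**Working it through.** **The plan's own figure.** The documents give no SD, effect size or power for vital signs. The only design figure is the 1,520 patients for the primary composite (protocol 9.7: 80% power, two-sided 5%, common odds ratio 0.75). It supplies the arm size, so I checked it first.

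- Placebo distribution from protocol 6.4.3: failure 11.9%, success 26.0%, hence unchanged 62.1%.
- Serelaxin at odds ratio 0.75: 9.2%, 58.9%, 31.9% (failure, unchanged, success).
- Mean category probabilities: 0.1055, 0.6050, 0.2895. Their cubes sum to 0.247.
- Whitehead's formula: N = 12(1.960 + 0.842)² / [ln(0.75)² × (1 - 0.247)] = 1,512 after rounding up. Power at 1,520 is 80.2%.

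The stated figure reproduces, and the design is not in question. At 1:1 allocation there are 760 patients per arm.

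**Formulas.** Let the baseline SD be 1, the follow-up SD be k and the correlation be rho. The slope of follow-up on baseline is b = rho × k. Up to the common factor 2/n for n patients per arm, the variances of the between-arm difference are:

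- change score: k² + 1 - 2 rho k
- ANCOVA: k²(1 - rho²)
- excess of the change score over ANCOVA: (1 - rho k)² = (1 - b)²

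The excess is never negative and is zero only when b = 1. With equal SDs (k = 1) the ratio of ANCOVA to change-score variance is (1 - rho²)/[2(1 - rho)] = (1 + rho)/2, and the confidence interval shrinks by 1 - √[(1 + rho)/2].

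**Results, k = 1, 760 per arm.** Rho is an assumption, so a range is shown. The last column is the ANCOVA power for an effect that the t-test would detect with 80% power.

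| rho | ANCOVA / t-test variance | CI narrower by | ANCOVA power |
|---|---|---|---|
| 0.3 | 0.65 | 19.4% | 93.5% |
| 0.5 | 0.75 | 13.4% | 89.9% |
| 0.7 | 0.85 | 7.8% | 86.0% |
| 0.8 | 0.90 | 5.1% | 84.0% |
| 0.9 | 0.95 | 2.5% | 82.0% |
| 0.95 | 0.975 | 1.3% | 81.0% |

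**Unequal SDs.** What matters is the slope, not the correlation alone. At rho = 0.8 and k = 0.8 the slope is 0.64, and the t-test variance is 1.56 times the ANCOVA variance. At rho = 0.8 and k = 1.25 the slope is 1 and the two are equal.

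**Simulation check.** With 3,000 replicates at 760 per arm and no true effect, the t-test/ANCOVA variance ratio was 1.37 at rho 0.5 (theory 1.33) and 1.14 at rho 0.8 (theory 1.11). Both estimators averaged essentially zero, so neither is biased.

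**Absolute scale.** For illustration, assume a pulse SD of 15 bpm. The 95% half-width is 1.96 × 15 × √[2 × 2(1 - rho)/760] for the t-test and 1.96 × 15 × √[2(1 - rho²)/760] for ANCOVA. This gives 1.8 against 1.4 bpm at rho 0.3, and 1.5 against 1.3 bpm at rho 0.5.

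**The case against.** The strongest reply is that nothing here is an error. The change score already removes the baseline, the t-test is unbiased under randomization, and the protocol and SAP agree. The comparisons are unpowered safety analyses outside the testing hierarchy. With 760 per arm the intervals are already short; under the assumed pulse SD the gain is 0.2 to 0.35 bpm. The correlations are assumed, and early readings such as pulse at 6 and 12 hours may track baseline more closely than later ones, so one low value of rho should not be applied to every time point. All of this stands, and it is why the point is minor. It does not favour keeping the t-test, since ANCOVA is no less precise in large 1:1 samples.

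Three stronger readings are tempting but unsupported.

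- **That baseline is ignored.** It is not; it is subtracted with coefficient 1. What is missing is the covariate.
- **That the effect of a vasodilator on blood pressure is poorly tested as a result.** Blood pressure is not in the t-test list. Protocol 9.5.2 and SAP 2.4.5 handle it through confirmed blood-pressure-decrease events, and SAP 2.4.1.2 adds odds ratios with confidence intervals for hypotension.
- **That the biomarker objective suffers from the same fault.** Protocol 9.5.8 says "Summary statistics for the baseline values, the post-baseline values, and the change from baseline will be provided by treatment group", and SAP Table 2-5 says "Summary statistics, see Section 2.2.3". But SAP section 2.2.3 refers the details to a separate biomarker analysis plan that was not available for review. Neither document plans a test of raw biomarker change, so no loss of power can be charged to one.

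**Conclusion.** The point holds as a minor efficiency matter for the listed vital signs. The change-score t-test is valid but gives up precision wherever the slope of follow-up on baseline differs from 1. With equal SDs, ANCOVA has 65% to 97.5% of the t-test variance as rho runs from 0.3 to 0.95. The gain may be worth having for pulse, respiratory rate and temperature if they track baseline weakly. It is close to nil for weight, whose correlation I would expect to be near 0.95. The size rests on assumed correlations and on equal SDs; the direction does not. No bias and no inconsistency between the documents is shown, and no primary or secondary conclusion changes.

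**What to change.** In protocol 9.5.2 and SAP 2.4.3, replace the t-test sentence by wording such as: *At each time point the change from baseline will be analyzed by ANCOVA with treatment as factor and the baseline value as covariate. A missing baseline will be replaced by the last screening value as in SAP section 2.1.3. The adjusted mean difference and its 95% confidence interval will be reported.* Keep the descriptive tables unchanged.

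The cost is this short replacement text in each document and one covariate already in the database. No new data are needed, and the method is already in the plan for VAS-AUC. Given the screening fallback, the covariate itself should remove no patient who would have had a change score. Make the change before unblinding so that the analysis remains pre-specified.

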### **9.5.3 Resource utilization**

Summary statistics on hospital length of stay in index ICU/CCU for the initial and subsequent hospitalizations, as well as procedures rendered during these hospitalizations will be provided by treatment group. Additional information will be provided in the Statistical Analysis Plan.

### **9.5.4 Health-related Quality of Life**

Health related quality of life assessments will not be collected in this study.

### **9.5.5 Pharmacokinetics**

Steady state concentration (Css) will be estimated based on the serum concentration determined at the 48 hr time point prior to the end of infusion. Systemic clearance will be calculated using the rate of infusion and Css for each patient as indicated below:

$$\text{Clearance (mL/hr/kg)} = \text{Rate of infusion (\mu g/kg/hr)} / \text{Css (\mu g/mL)}.$$

Since only sparse PK time points for serelaxin serum concentration will be collected, no other PK parameters will be determined in this study.

Concentrations below the assay LLOQ (BLQ) will be treated as zero for PK parameter calculations.

Descriptive statistics for serelaxin concentrations will be listed by time points (for baseline and 48hr samples only) to include arithmetic mean, geometric mean with its corresponding 90% confidence interval, median, SD, CV, min and max. A value of "0" will be used for samples that are BLQ in these calculations and therefore be excluded from geometric mean calculations. Descriptive statistics include arithmetic mean, geometric mean with its corresponding 90% confidence interval, median, SD, CV, min and max will also be provided for the two PK parameters, Css and clearance.

Subgroup analysis on Css and CL to assess the potential effects of various extrinsic and intrinsic factors on the PK of serelaxin may be performed as appropriate. These factors may include but not limited to age, gender, race, country of origin, concomitant medications, etc. Details of these analyses will be described in the Statistical Analysis Plan.

Serelaxin serum concentration will be assayed in Day 60 samples as well, in order to demonstrate the lack of drug interference with the immunogenicity assay, but this data will be included only as part of the immunogenicity results but not in the PK results.

### **9.5.6 Immunogenicity**

Anti-serelaxin antibodies will be measured in serum samples collected at the Day 60 time point. To account for individual variability in background of each subject and to check for endogenous interference and/or pre-existing anti-serelaxin antibodies, anti-serelaxin antibodies will also be measured at baseline. Frequencies and percentages will be computed for occurrence of anti-RLX030 antibodies at each time point. Listings for subjects with a

positive screening result at any time point will include subject number, time point, immunodepletion result, titer, and neutralizing antibody result.

#### **9.5.7 Pharmacogenetics/pharmacogenomics**

Not applicable

#### **9.5.8 Biomarkers**

Summary statistics for the baseline values, the post-baseline values, and the change from baseline will be provided by treatment group for the FAS and Safety Set.

#### **9.5.9 PK/PD**

Not applicable

[figure not shown]
[figure not shown]
### **9.6 Interim analyses**

It is planned to establish an external and Independent Data Monitoring Committee (DMC) to monitor patient safety data on a regular basis during the course of the study. For this study, it is likely DMC will review safety data in a regular frequency, e.g., every six months. DMC may request additional safety data review. Such safety analyses do not inflate the type I error for the primary efficacy hypothesis testing and thus require no multiplicity adjustments.

There will be no formal efficacy interim analysis.

### **9.7 Sample size calculation**

A sample size of 1,520 AHF patients will need to be randomized 1:1 to serelaxin and placebo. This study will have 80% power at a two-sided type-I error of 5% to detect a distributional shift with a common odds ratio of 0.75 between the distributions of placebo and serelaxin

The sample size re-estimation is anticipated to be conducted when about 70% of patients have enrolled and the event rates will be calculated based on patients who have data at least through Day 5. If the pooled observed event rates of treatment failure and treatment success

(assessed on a blinded basis) are much lower than expected based on RELAX-AHF data, sample size may be increased to preserve the target study power.

